3.4.1.2. Study Medication Discontinuation

Study medication should be permanently discontinued in the event of any of the following:

- Severe infection requiring parenteral antimicrobial therapy or hospitalization
- Symptomatic herpes zoster
- Malignancy
- Anaphylactic or severe allergic reaction

Date: 09NOV2018, Version 1.0 Page 24 of 80 CONFIDENTAL

• WBC Count: $< 1 \times 10^3/\mu$ L or second occurrence of $< 2 \times 10^3/\mu$ L

- ANC: $< 0.5 \times 10^3/\mu L$ or second occurrence of $< 1 \times 10^3/\mu L$
- Lymphocyte count: $< 0.3 \times 10^3/L$ or second occurrence of $< 0.5 \times 10^3/\mu L$
- Platelet count: $< 50 \times 10^3/\mu L$ or second event of $< 75 \times 10^3/\mu L$ in each case, value should be confirmed by retesting before treatment discontinuation
- Hemoglobin: < 6.5 g/dL or second occurrence of < 8 g/dL in each case, value should be confirmed by retesting before treatment discontinuation
- AST or ALT:

Protocol: ATI-502-AA-203

- > 5 x ULN persisting for 2-weeks of study medication interruption or second event of > 5 x ULN
- > 3 x ULN with total bilirubin >2 x ULN or symptoms of hepatocellular injury [fatigue, nausea, vomiting, right upper quadrant pain or tenderness, fever, rash and/ or eosinophilia (>5%)].
- Serum creatinine: > 2 x ULN persisting for >2 weeks of treatment discontinuation or second occurrence of > 2 x ULN

The continued treatment of subjects who experience other serious or severe adverse events considered related to study treatment should be discussed with the Sponsor's medical monitor.

Site staff must perform protocol-required procedures for trial discontinuation and follow-up.

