3.4.1. Safety Criteria for Adjustment or Stopping Doses

3.4.1.1. Study Medication Interruption

Protocol: ATI-502-AA-203

Treatment with ATI-502 Topical Solution should be temporarily interrupted in the event of severe adverse events considered related to ATI-502, or in the event of one or more of the abnormal laboratory values listed in Table 2.

Table 2: Study Medication Interruption Criteria

Laboratory Test	Hold Study Medication if:	Resume Study Medication if:
WBC count	$< 2 \times 10^{3}/\mu L$	$\geq 2.5 \times 10^{3}/\mu L$
ANC	$< 1 \times 10^{3}/\mu L$	$\geq 1.5 \times 10^{3}/\mu L$
Lymphocyte count	$< 0.5 \times 10^{3}/\mu L$	$\geq 0.75 \times 10^{3}/\mu L$
Platelet count	$< 75 \times 10^3 / \mu L$	Returns to Baseline values
Hemoglobin	< 8 g/dL or a decrease > 2g/dL (from baseline value on ATI- 501-AUAT-201)	$\geq 10 \text{ g/dL}$
AST or ALT	> 3 x ULN	< 2 x ULN or within 20% of Baseline values
Serum creatinine	>2 x ULN	<1.5 x ULN or within 10% of Baseline value

Subjects with one or more of laboratory values meeting the Study Medication Interruption Criteria found in Table 2 must have repeat lab testing performed with results meeting the minimum criteria for resumption in order to initiate treatment

During treatment, if a subject has one or more of the abnormal laboratory values noted in Table 2, the investigator or designee upon receipt and review of the central laboratory report should instruct the subject to hold study medication dosing. The investigator or designee should ask the subject about symptoms, concomitant illnesses and medications and repeat the test(s) as soon as possible. The Medical Monitor must be notified of dose interruptions due to SAEs considered related to study medication or laboratory abnormalities noted in Table 2.

If the retest confirms the abnormal laboratory value, then the study medication should continue to be held followed by repeat testing once a week or sooner at the discretion of the investigator. The subject should be followed until the laboratory abnormality(s) returns to normal or to Baseline (Visit 1) values.

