8.1.5. Clinical Laboratory Assessments

A qualified staff member will collect non-fasting samples for clinical laboratory analysis at the visits detailed in Schedule of Assessments (Table 3). Samples will be sent to a central laboratory for analysis. Refer to the study specific laboratory manual for handling and shipping instructions. The following tests will be conducted:

Chemistry Panel

Albumin

Alkaline phosphatase

Alanine aminotransferase (ALT)

Aspartate aminotransferase (AST)

Blood urea nitrogen (BUN)

Bicarbonate

Calcium

Chloride

Creatinine

Glucose

Lactate dehydrogenase (LDH)

Phosphorus

Potassium

Sodium

Total bilirubin

Total protein

Uric acid

CPK

Crk

Total cholesterol, LDL, HDL,

Triglycerides

Urine Pregnancy Test for WOCBP

(At the visits detailed in Schedule of

Assessments (Table 3)).

Complete Blood Count

Hematocrit

Hemoglobin

Platelet count

Red blood cell morphology

Red blood cell count

White blood cell count

White blood cell differential

% & absolute

Basophils

Eosinophils

Lymphocytes

Monocytes

Neutrophils

Urinalysis

Total cholesterol, LDL, HDL and Triglycerides will be assessed at all visits. The results of the clinical laboratory tests will be reported on the central laboratory's standard reports. The investigator must note NCS or CS to define the clinical relevance of any result that is outside the normal range for the laboratory. The investigator must date and initial every laboratory report.

Date: 09NOV2018, Version 1.0 Page 47 of 80 CONFIDENTAL

The investigator or subinvestigator must review all the laboratory test results against the study entry criteria and the Study Medication Interruption Criteria Table 2 for each subject. Subjects with laboratory values meeting the Study Medication Interruption Criterial found in Table 2 must have repeat laboratory testing performed with results meeting the minimum criteria for resumption.

The investigator must report all laboratory results from samples collected on the ATI-502-AA-203 study that are BOTH outside the normal range for the laboratory AND, in the opinion of the investigator, CS as an AE. Laboratory results from samples collected at V9 on the ATI-501-AUAT-201 study that are BOTH outside the normal range for the laboratory AND, in the opinion of the investigator, CS must be reported as medical history on the ATI-502-AA-203 study eCRF. The investigator must review all laboratory reports in a timely manner.

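### The single-value lymphocyte stop in Section 3.4.1.2 is written per litre, 10^6 below the same digits per microlitre, so no non-zero count can trigger it

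*Combined protocol and SAP*

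**What the plan says.** Section 3.4.1.2 lists the laboratory values at which study medication is stopped for good. The lymphocyte line reads "Lymphocyte count: $< 0.3 \times 10^3/L$ or second occurrence of $< 0.5 \times 10^3/\mu L". It has two limbs, a single-value limit and a limit for a repeated occurrence, and the two carry different units.

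The neighbouring lines have the same two-limb form with one unit throughout:

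- White cells, with both limbs per microlitre: "WBC Count: $< 1 \times 10^3/\mu$ L or second occurrence of $< 2 \times 10^3/\mu$ L"
- Platelets, with both limbs per microlitre: "Platelet count: $< 50 \times 10^3/\mu L$ or second event of $< 75 \times 10^3/\mu L"
- Neutrophils, with both limbs per microlitre: "ANC: $< 0.5 \times 10^3/\mu L$ or second occurrence of $< 1 \times 10^3/\mu L"

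Table 2 in Section 3.4.1.1 sets the temporary hold for lymphocytes at below 0.5 × 10^3/µL and allows dosing to resume at 0.75 × 10^3/µL or above. The same section adds: "The Medical Monitor must be notified of dose interruptions due to SAEs considered related to study medication or laboratory abnormalities noted in Table 2".

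Under Section 8.1.5, the responsible site clinician "must review all the laboratory test results against the study entry criteria and the Study Medication Interruption Criteria Table 2". Table 2 does not contain the 0.3 limit, and no other section restates it. Section 3.4.1.2 is the only place a site can find this rule.

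**The concern.** A single-value stop should act on a very low first result without waiting for a second. As written, the lymphocyte limit lies far below any non-zero count a laboratory could report, so that limb does nothing unless the count is reported as zero.

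What changes is the handling of a subject whose first low lymphocyte value is above zero but below 0.3 × 10^3/µL. If the limit is per microlitre, that subject stops permanently. If the text is followed literally, the subject meets only the Table 2 hold: dosing is interrupted, the test is repeated, the Medical Monitor is told, and dosing may restart once the count recovers to 0.75 × 10^3/µL. The platelet and hemoglobin lines ask for a confirming retest before discontinuation and the lymphocyte line does not, which suggests that its single-value limb was meant to act on the first result.

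The parameter is relevant to this drug. Section 1.1 describes JAK1 and JAK3 signalling as driving lymphocyte activation and proliferation. Subjects may enter directly from 24 weeks of the oral prodrug of the same inhibitor, at up to 800 mg twice daily (Sections 1.5 and 1.6).

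**Working it through.** The limit is a bare threshold, not derived from other inputs, so there is no calculation of the plan's to reproduce. The check is a unit conversion, a count of the comparable limits, and a comparison with the other cell lines.

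**1. Convert the written limit.** 1 L = 10^6 µL.

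- As written: 0.3 × 10^3/L = 300 cells/L = 300 / 10^6 = 0.0003 cells/µL.
- Same digits per microlitre: 0.3 × 10^3/µL = 300 cells/µL.
- Ratio: 300 / 0.0003 = 10^6.

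**2. Count the other numeric blood-cell limits and their units.**

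| Source | WBC | ANC | Lymphocytes | Platelets | Total | Unit |
|---|---|---|---|---|---|---|
| Table 2 (hold and resume) | 2 | 2 | 2 | 1 | 7 | all per µL |
| Section 3.4.1.2, excluding the limit in question | 2 | 2 | 1 | 2 | 7 | all per µL |

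The platelet resumption rule in Table 2 is a return to baseline and has no number, hence 1 in that cell. The total is 7 + 7 = 14, all per microlitre. The single-value lymphocyte limit is the only one per litre.

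**3. Compare each single-value stop with its hold limit** (× 10^3/µL).

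| Cell line | Single-value stop | Hold | Stop / hold |
|---|---|---|---|
| WBC | 1 | 2 | 0.50 |
| ANC | 0.5 | 1 | 0.50 |
| Platelets | 50 | 75 | 0.67 |
| Lymphocytes, if per µL | 0.3 | 0.5 | 0.60 |
| Lymphocytes, as written | 0.0000003 | 0.5 | 0.0000006 |

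Read per microlitre, the lymphocyte ratio falls between those of the other cell lines. As written it does not resemble them.

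**4. Can the written limit be met?** The protocol does not give the laboratory's reporting precision. Assume counts are reported to 0.01 or to 0.1 × 10^3/µL.

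- At 0.01 × 10^3/µL, the smallest non-zero report is 10 cells/µL = 10^7/L, and 10^7 / 300 is about 33,000 times the written limit.
- At 0.1 × 10^3/µL, it is 100 cells/µL = 10^8/L, and 10^8 / 300 is about 333,000 times the written limit.

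At either precision, only a reported zero triggers the limb.

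**5. Which results are handled differently?** First values above 0 and below 0.3 × 10^3/µL. Values from 0.3 up to but not including 0.5 × 10^3/µL lead to a hold under either reading.

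**The case against.** **It may not be in the source.** The point rests on one character, and converting a PDF to text can lose a micro sign. Small character faults do appear elsewhere in the text, for example in the facial-hair assessment in Section 7.2.2, and the WBC line of this same list is spaced differently from the ANC line. This cannot be ruled out. It is unlikely, because the sign survives in all 14 other limits, including the second limb of the same line. It does mean the source page must be checked first.

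**Readers would correct it.** The literal value is physiologically meaningless and the surrounding lines make the intent plain, so an experienced investigator may well read 0.3 × 10^3/µL. That is fair, but a permanent-stop rule should not depend on its readers repairing the units, and the line could be copied unchanged into site tools or laboratory alerts.

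**Other rules cover most of the gap.** This is largely right. A value below 0.5 × 10^3/µL still brings a hold, a prompt repeat, Medical Monitor notification and, if confirmed, continued interruption with testing at least weekly. A second occurrence below 0.5 × 10^3/µL stops treatment. The WBC, severe-infection and herpes zoster stops apply, and Section 4.3 lets the investigator remove a subject. A clinically significant abnormal result must also be reported as an adverse event (Section 8.1.5). What remains is rechallenge after one deep value that recovers. Once dosing resumes, scheduled blood counts fall at Weeks 4, 8, 16, 24 and 28 (Table 3), up to 8 weeks apart on treatment, so the second-occurrence rule is a weaker substitute for stopping at the first value.

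**The factor of 10^6 describes the slip, not the harm.** Agreed. The documents give no expected frequency of such counts, so the number of subjects affected cannot be estimated.

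**Conclusion.** The concern holds. As written, the single-value lymphocyte limit is 10^6 below the same digits in the unit used for the other 14 count limits, no non-zero reportable count meets it, and nothing else in the protocol corrects it. The intended limit is almost certainly 0.3 × 10^3/µL, or 60% of the hold limit.

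This is a wrong threshold in a safety stopping rule and should be fixed. The consequence is bounded: it is limited to possible rechallenge in subjects whose first low value is above 0 and below 0.3 × 10^3/µL and who then recover to at least 0.75 × 10^3/µL. Confidence is medium, because the conclusion assumes that the source page shows the litre unit.

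**What to change.** 1. Check the source page of Section 3.4.1.2 to confirm that the unit is printed as /L.
2. Confirm the intended limit with the medical monitor.
3. Correct the line so that it stops treatment at a lymphocyte count < 0.3 × 10^3/µL, or at a second occurrence of < 0.5 × 10^3/µL.
4. Notify the sites, approximately 25 under Section 3.2.

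The edit is one character plus a site notice. Section 12.1 requires IRB/EC approval of amendments before use, and a change to a safety limit may not count as the logistical or administrative change allowed by Section 12.4, so that approval step may have to be added. No change to sample size, assessments or analysis follows.

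### One limb of the creatinine permanent-stop rule is circular as worded, and in three Table 2 rows a single value can meet both hold and resume

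*Combined protocol and SAP*

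**What the plan says.** **Permanent stop (Section 3.4.1.2).** The list opens: "Study medication should be permanently discontinued in the event of any of the following". The creatinine item has two alternative limbs, both at > 2 x ULN: "persisting for >2 weeks of treatment discontinuation or second occurrence of" that level. The first AST/ALT item has the same structure at > 5 x ULN, but its wording is "persisting for 2-weeks of study medication interruption or second event of" that level.

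**Hold and resume (Section 3.4.1.1, Table 2).**
- AST/ALT: hold above 3 x ULN; resume at "< 2 x ULN or within 20% of Baseline values".
- Creatinine: hold above 2 x ULN; resume at "<1.5 x ULN or within 10% of Baseline value".
- Hemoglobin: hold below 8 g/dL, or after a fall of more than 2 g/dL ("from baseline value on ATI- 501-AUAT-201"); resume at 10 g/dL or above.

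**Text under Table 2.** A subject who already meets a hold limit before treatment must be retested, with "results meeting the minimum criteria for resumption in order to initiate treatment". During treatment, a retest that confirms the abnormal value keeps the drug on hold with repeat testing at least weekly. Follow-up runs until the abnormality "returns to normal or to Baseline (Visit 1) values".

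**The concern.** Sites have to apply these rules as they stand, and two features prevent a single reading.

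First, the creatinine item makes a permanent stop depend on an elevation that lasts through a period of discontinuation. If that word means the permanent stop, the limb can apply only to someone already stopped.

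Second, a hold limit and a resume limit should leave no value on both sides. The AST/ALT and creatinine rows each offer a resume route tied to the subject's own baseline with no ceiling at the hold limit. The hemoglobin row sets a relative hold against an absolute resume level.

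At stake is whether a particular subject is kept off drug, restarted or stopped for good. If about 25 sites settle this differently, the interruptions and discontinuations that they record will not mean the same thing across sites.

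**Working it through.** The plan states no figure to reproduce. The check is a comparison of terms, followed by threshold arithmetic.

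**1. Terms in the stop rules.** Section 3.4.1.1 calls the temporary action an interruption or a hold. In Section 3.4.1.2 the platelet and hemoglobin items ask for a confirmatory retest ahead of treatment discontinuation, where the term means the permanent stop. The AST/ALT item uses interruption for the temporary state. By the section's own vocabulary, the first creatinine limb is circular.

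The practical difference appears in one case. A subject's first creatinine above 2 x ULN stays there for more than 2 weeks on hold and then falls below 1.5 x ULN.
- If the limb means interruption, the permanent stop has already been triggered.
- Read literally, it has not been triggered, and Table 2 allows resumption.

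**2. AST/ALT and creatinine overlap.** Let B be baseline in multiples of ULN, and read within 20% (10%) of Baseline as up to 1.2B (1.1B). The upper resume limit is max(2, 1.2B) for AST/ALT and max(1.5, 1.1B) for creatinine.
- AST/ALT passes the hold limit when 1.2B > 3, that is B > 3/1.2 = 2.50.
- Creatinine passes the hold limit when 1.1B > 2, that is B > 2/1.1 = 1.82.

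| Test | B (x ULN) | Upper resume limit (x ULN) | Hold above (x ULN) | Overlap |
|---|---|---|---|---|
| AST/ALT | 1.0 | 2.00 | 3 | no |
| AST/ALT | 2.4 | 2.88 | 3 | no |
| AST/ALT | 2.6 | 3.12 | 3 | yes |
| AST/ALT | 3.0 | 3.60 | 3 | yes |
| Creatinine | 1.0 | 1.50 | 2 | no |
| Creatinine | 1.8 | 1.98 | 2 | no |
| Creatinine | 1.9 | 2.09 | 2 | yes |
| Creatinine | 2.0 | 2.20 | 2 | yes |

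With B = 2.0, a creatinine between 2.0 and 2.2 x ULN meets the resume limit while lying above the level in the second-occurrence limb of the stop rule.

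**3. Can such baselines enter?** Sections 4.1 and 4.2 give no numeric AST/ALT or creatinine limit, and Section 8.1.5 has results reviewed against the entry criteria and Table 2. Baselines from 2.50 to 3.00 x ULN (AST/ALT) or 1.82 to 2.00 x ULN (creatinine) do not reach a hold limit, so the pre-treatment retest does not catch them. Above the hold limit, the retest is judged by the same resume limits. If Baseline is the abnormal value itself, AST/ALT of 3.5 x ULN could pass at up to 1.2 x 3.5 = 4.2 x ULN.

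**4. Which baseline?** The hemoglobin row names the parent study and the follow-up sentence names Visit 1 of this study. The AST/ALT and creatinine rows name neither.

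**5. Hemoglobin.** With parent-study baseline H in g/dL, the relative hold applies below H − 2 and resumption is allowed at 10 or above. Both hold for values from 10 up to H − 2, which requires H > 12. For H = 14, a value of 11.5 is a fall of 2.5 g/dL (hold) and is above 10 (resume). The overlap runs from 10 up to 12 g/dL.

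**6. Rows without conflict** (x 10³/µL): WBC (hold < 2, resume ≥ 2.5), ANC (< 1, ≥ 1.5) and lymphocytes (< 0.5, ≥ 0.75).

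**The case against.** The best reply is that the surrounding text already protects subjects. Creatinine above 2 x ULN requires a hold under Table 2, and a confirmed value keeps the drug on hold with weekly or earlier retests and notice to the Medical Monitor. A persistent first elevation is therefore already off drug. The AST/ALT item makes it likely that interruption was meant. This stands, and it rules out an inference that a reader might draw, that the creatinine stop cannot fire or that its wording affects every subject. The second-occurrence limb works as written, and the first matters only when a first elevation persists. What remains open is whether that subject may later resume.

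On the overlap, one can argue that a retest still above the hold limit simply continues the hold. That is a natural reading, but the protocol does not say that the hold column prevails. For hemoglobin it would leave the 10 g/dL resume level without effect in anyone whose baseline exceeds 12 g/dL.

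It is also fair to say that high baselines may rarely reach this study. Inclusion 7 requires good general health in the investigator's opinion. Inclusion 4 and exclusion 1 bar subjects who met the parent study's discontinuation criteria. Those criteria are not shown here, so the point limits the likely size of the AST/ALT and creatinine overlap without removing it.

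Finally, it would be too broad to conclude that the laboratory rules fail as a set, given the rows in step 6 of the working.

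**Conclusion.** Both inconsistencies are in the operative text, and both are limited in scope.

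- **Creatinine stop:** one of two limbs is circular if read literally. The consequence is confined to the later status of a subject with a first, persistent elevation, and there is no evident gap in holding the drug.
- **AST/ALT and creatinine resume limits:** the overlap needs a baseline above 2.50 x ULN or 1.82 x ULN respectively. It is probably uncommon. The documents give no baseline laboratory distribution, so no frequency can be stated.
- **Hemoglobin:** the overlap needs only a parent-study baseline above 12 g/dL, so it does not depend on grossly abnormal baseline values as the other two do.

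The AST/ALT and creatinine results assume that the percentage limbs extend upward from baseline, and that no parent-study limit outside these documents excludes the baselines concerned. The conclusion is that the passages conflict. Which threshold is right is not at issue here.

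**What to change.** 1. Reconcile the creatinine item in Section 3.4.1.2 with the terms used in Section 3.4.1.1 and in the AST/ALT item, so that it is clear which off-drug period is counted and whether a subject with a first, persistent elevation may resume.
2. Reconcile the hold and resume columns of Table 2 for AST/ALT, creatinine and hemoglobin so that no value satisfies both, or state which column prevails.
3. State for every row, and for the pre-treatment retest, whether Baseline means the parent study's baseline or Visit 1 of this study.

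The sponsor sets the thresholds. The cost is protocol wording and the IRB/EC approval that any amendment needs. No new data, assessments or changes to the analysis are required.

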3.5. Criteria for Study Termination

This study may be terminated prematurely in whole or in part due to a change in the benefit/risk profile for ATI-502 Topical Solution such that continuation of the study would not be justified on medical or ethical grounds. This determination may be made by the Study Investigators in conjunction with the Sponsor, or by IRB or the U.S. Food and Drug Administration (FDA). The Sponsor may also elect to terminate the study if ATI-502 development is discontinued.

If the study is terminated prematurely, the Sponsor will notify the Study Investigators and the FDA. The Investigator must promptly notify all enrolled subjects and the IRB of study termination.

3.6. Study Procedures

The investigator, a designated and appropriately trained staff member, or the subject will perform the study assessments according to the Schedule of Assessments (Table 3). The same staff member should perform the assessments for a given subject throughout the study. If this becomes impossible, an appropriate designee with overlapping experience with the subject and study should perform the assessments. The same lighting conditions and subject positioning should be used for all evaluations for a given subject.

Date: 09NOV2018, Version 1.0 Page 25 of 80 CONFIDENTAL

Table 3: Schedule of Assessments

Protocol: ATI-502-AA-203

		Visit 9 ¹ from Study							Post- Treatment
Assessi	ments	ATI-501- AUAT-201	Visit 1 ¹	Visit 2	Visit 3	Visit 4	Visit 5	Visit 6 (ET)	Visit 7
12.12.2.12.12	Week	NA	0	2	4	8	16	24	28
	Treatment Day	NA	1	15	29	57	113	169	197
	Treatment Window(days)	N/A	N/A	± 3	± 3	± 3	± 3	± 3	± 7
	ed consent ²		X						
	on/exclusion criteria		X						ļ
	ıl exam ³	✓	(X) [^]					X	
	raphics and Medical History Update		X						
	ia Areata History (Transcribe)		X		37	77	37	37	77
Vital si		√	(X) [^]		X	X	X	X	X
	l CBC, Chemistry, Urinalysis	·			X	X	X	X	X
	regnancy test ⁵	✓	(X) [^]		X	X	X	X	X
ECG		✓							
	Alopecia Scalp Appearance Assessment (ASAA-AAP: SR or ASAA-AT/AU: SR)	√	(X) [^]			X		X	X
	Alopecia Facial Hair Appearance Assessment (AFHA: SR)	✓	(X) [^]			X		X	X
يو ا	Subject Global Impression of Severity (SGIS-AAP or SGIS-AT/AU)	✓	(X) [^]			X		X	
Subject ⁶	Alopecia Impact Assessment (AIA): Subject Rating	✓	(X) [^]			X		X	
~	Subject Global Impression of Change (SGIC) ⁷	✓						X	
	Subject Global Impression Treatment Satisfaction (SGITS-AAP or SGITS-AT/AU) ⁸	√	(X) [^]			X		X	
	Subject Global Satisfaction with Hair Quality (SGSHQ-AAP or SGSHQ-AT/AU)	✓	(X) [^]			X		X	
	Alopecia Scalp Appearance Assessment (ASAA: - AAP:CR of ASAA-AT/AU:CR)	✓	(X) [^]			X		X	X
Investigator ⁶	Alopecia Facial Hair Appearance Assessment (AFHA: CR)	✓	(X) [^]			X		X	X
tig	Non-Scalp Hair Loss Assessment (NSHA)	✓	(X) [^]			X		X	
Inves	Physician Global Impression of Severity (PhGIS-AAP or PHGIS-AT/AU)	✓	(X) [^]			X		X	
1	Physician Global Impression of Change (PhGIC)	✓	(X) [^]					X	
	Hair Quality Assessment (Patchy AA Subjects Only) ⁹	✓	(X) [^]			X		X	X

Assessments	Visit 9 ¹ from Study ATI-501- AUAT-201	Visit 1 ¹	Visit 2	Visit 3	Visit 4	Visit 5	Visit 6 (ET)	Post- Treatment Visit 7
SALT Score (prior to ALODEX) ¹⁰	✓	(X) [^]		X	X	X	X	X
ALODEX Score (after SALT) ¹¹	✓	(X) [^]		X	X	X	X	X
Vellus and Indeterminate Hair Assessment	✓	(X) [^]		X	X	X	X	X
Photography (complete scalp)	✓	(X) [^]		X	X	X	X	
Subject instructions ¹²		X	X	X	X	X		
In office study medication application		X						
Dispense study medication ¹³		X	X	X	X	X		
Collect study medication and assess compliance ¹⁴			X	X	X	X	X	
Concomitant therapies	√	(X) [^]	X	X	X	X	X	X
Adverse events	√	(X) [^]	X	X	X	X	X	X

Abbreviations: CR= Clinician Rating; ET= Early termination Visit; SR= Subject Rating

¹Visit 1 will occur on the same day as Visit 9 of study ATI-501-AUAT-201. Visit 9 procedures for study ATI-501-AUAT-201 must be completed prior to initiation of any study related activity for ATI-502-AA-203. Eligible subjects must sign consent prior to first application of topical study medication. The assessments performed for Visit 9 in study ATI-501-AUAT-201 will be entered into the source document and eCRF for Visit 1 in study ATI-502-AA-203. ATI-502-AA-203 enrollment may not be open at the time of a subject's ATI-501-AUAT-201 Visit 9. If this scenario occurs, the subject may be brought back to the clinic prior to their ATI-501-AUAT-201 Visit 10. At this visit, the subject will then be given topical treatment. Assessments marked as (X)^ represent repeat assessments that would need to be performed if the subject cannot enroll directly at Visit 9 (or within 14 calendar days of Visit 9) from study ATI-501-AUAT-201.

²A written, signed ICF must be obtained from each subject prior to performing any study related procedure.

³A physical examination includes: General appearance, examination of the head, eyes, ears, nose and throat, respiratory, cardiovascular, abdominal, extremities, musculoskeletal, lymphatic, skin (other than AA) and neurological assessment.

⁴Vital signs include oral or ear temperature, blood pressure, heart rate, respiration rate.

⁵ For WOCBP, the UPT performed at Visit 9 in study ATI-501-AUAT-201 must be negative prior to study medication application. UPT in WOCBP must also be obtained at Visits 3, 4, 5, 6, and 7 and must be negative for the subject to continue in the study.

⁶ The subject should perform assessments prior to the Investigator assessments. The investigator may assist the subject in locating a Target Patch.

⁷The subject should refer to the Baseline (Visit 2 from ATI-501-AUAT-201 and Visit 1 from ATI-502-AA-203) photographs when assessing the change over time.

⁸The study staff should remind the subject that this question is in relation to the satisfaction with the result of the hair regrowth.

⁹In subjects with patchy AA, the assessment of hair quality will be performed at the edge of the target patch. For subjects with AU/AT, the assessment of hair quality will be recorded as Not Applicable in the source document and eCRF. At Baseline (Visit 1), the assessment should be determined prior to the first dose of study medication.

¹⁰SALT score must be determined prior to ALODEX using device provided.

¹¹ALODEX score determined after SALT score using device provided.

¹²The study staff must instruct the subject to apply study medication according to the instructions in Appendix 13 and Appendix 14.

	Visit 9 ¹ from Study							Post- Treatment
	ATI-501-	Visit 1 ¹	Visit 2	Visit 3	Visit 4	Visit 5	Visit 6	Visit 7
	AUAT-201						(ET)	
Assessments				22 4 4 4		4 04		

¹³Each study medication bottle contains approximately 100 ml of ATI-502- Topical Solution. The study staff should dispense a number of bottles to each subject based on the quantity applied at the first visit.

¹⁴Staff should review the usage based on the number of used and unused bottles, weight of the bottle and counsel the subject as necessary.

